6 DEFINITIONS

- End of Study (EOS): Visit 6/Day 57 or Early Termination Visit
- Study Day: The study day is the day of study relative to the date of randomization (Baseline visit/Day 1).
Study Day = follow-up visit date – first dose date + 1
- Baseline: The baseline assessment is defined as the last non-missing measurement collected at Baseline visit prior to the test article application.

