9.1 Visit 1 (Day 1): Screening/Baseline

Subject can be screened up to 30 days prior to Baseline for those subjects that are qualified for enrollment, but require washout of prohibited medications and/or therapies. Screening and Baseline may be combined into a single visit for those subjects who do not require washout. Subjects who require washout for longer than 30 days will be reconsented.

At Screening, the investigator or designee will:

- Obtain a signed, written informed consent.
- Record demographics.
- Confirm inclusion/exclusion criteria.
- Record medical/dermatological history.
- Perform Fitzpatrick Skin Type Assessment (Section 10.3).
- Record prior and/or concomitant medications and therapies.

If the subject requires washout from previous medications, the remaining activities will be performed after washout is complete.

- Perform a brief physical exam, with vital signs (including height and weight).
- Perform a UPT for all WOCBP (Section 12.1). Results must be negative for the subject to be enrolled in the study.

- Designate the Treatment Area as a contiguous 25 cm² area on the face or scalp which contains at least four, but no more than eight clinically typical AKs, which are ≥ 4 mm in diameter. NOTE: Use the procedure as detailed in Appendix 1 to create and label the transparency to record the designated Treatment Area.
- Create a “subject specific” template to assist the subject in the identification of the Treatment Area prior to application of the study medication (Section 6.2).
- Perform AK lesion counts (Section 10.1). NOTE: AKs measuring ≥ 4 mm in diameter should be counted for inclusion/exclusion and must be between four and eight (inclusive), but smaller lesions should also be counted, recorded such the total of all AKs in the Treatment Area does not exceed eight AK lesions.
- Evaluate the size (i.e., diameter) of each AK lesion in the selected Treatment Area.
- Document LSRs (Section 10.2).
- Randomize the subject by assigning the next available (lowest) subject number in ascending order and dispense the corresponding test article kit.
- Review and dispense a Subject Instruction Sheet (Appendix 2) to the subject. Instruct the subject to apply the test article once per day for three consecutive days at home. NOTE: Application should not be immediately after a shower or within two hours of bedtime.

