- Demonstrate the proper test article application using the non-medicated samples provided for subject training and the provided Treatment Area template. Remind the subject to return all used and unused tubes of the test article at the next visit.
- Dispense the Subject Diary and provide completion instructions (Appendix 3).
- Record any AEs, if applicable.
- Schedule Visit 2/Day 4 follow-up visit.

9.2 Visits 2 (Day 4), 3 (Day 8 \pm 2), and 4 (Day 15 \pm 2): Follow-Up

At this visit, the investigator or designee will:

- Query the subject about any changes in health status since the previous visit, including concomitant medications and therapies, and document the findings.
- Use the transparency to locate the selected Treatment Area (Appendix 1).
- Document LSRs (Section 10.2).
- Collect all used and unused tubes of the test article and document in the Test Article Accountability Log [at Visit 2/Day 4].
- Collect the Subject Diary and review compliance [at Visit 2/Day 4].
- Schedule the next follow-up visit.

NOTE: Any “uncollected” test articles or subject diaries will be collected at Visit 3/Day 8.

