17.3 Statistical Methods

All statistical processing will be performed using SAS[®]. Summary tables (descriptive statistics and/or frequency tables) will be provided for baseline variables, efficacy variables, and safety variables. Continuous variables will be described by descriptive statistics (n, mean, median, standard deviation, minimum, and maximum). Frequency counts and percentage of subjects within each category will be provided for categorical data. Summaries will be provided for each treatment group.

Study Populations

The Safety population will include all randomized subjects who received the test article. The mITT population will include all randomized subjects who applied at least one dose of test article. The PP population will include all randomized subjects who met all the inclusion/exclusion criteria, were compliant with the assigned test articles (applied all three doses of the test article and no other evidence of material dosing noncompliance), completed the study within the designated visit window (± 2 days), and had no protocol violations that would affect treatment evaluation. Subjects who discontinued early from the study due to lack of treatment effect or who worsen and require alternate or supplemental therapy will be included in the PP population as treatment failures (non-responders). Subjects discontinued prematurely for other reasons will be excluded from the PP population, but included in the mITT population.

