5 STUDY SCHEDULE OF EVENTS

VISIT	Visit 1 ¹ Screening/ Baseline	Treatment Period (at home)	Visit 2 End of Treatment	Visit 3 Week 1	Visit 4 Week 2	Visit 5 Week 4	Visit 6 EOS ² Week 8
DAY	1	1-3	4	8 ± 2	15 ± 2	29 ± 2	57 ± 2
Informed Consent	X						
Demographics	X						
Inclusion/Exclusion	X						
Medical / Dermatological History	X						
Fitzpatrick Skin Type Assessment	X						
Brief Physical Exam ³	X						
Vital Signs ⁴	X						
UPT ⁵ for WOCBP ⁶	X						X
Definition of Treatment Area ⁷	X						
AK Lesion Count and Evaluation	X					X	X
LSR Assessment	X		X	X	X	X	X
Test Article Accountability: Dispense (D), Return (R)	D		R	R ⁸			
Subject Diary: Dispense (D), Return (R)	D		R	R ⁸			
Test Article Application		X					
Concomitant Medications and Therapies Review	X		X	X	X	X	X
Adverse Events	X		X	X	X	X	X

¹ Screening assessments may be performed up to 30 days prior to Baseline for those subjects that are qualified for enrollment, but require wash-out of prohibited medications and/or therapies. Screening and Baseline may be combined into a single visit for those subjects who do not require washout. Subjects who require washout for longer than 30 days will be re-consented.

² Or early discontinuation from the study.

³ Brief physical exam will include assessment of head and neck, cardiovascular, respiratory, gastrointestinal (abdomen), gross motor and gait.

⁴ Vital signs assessment will include height, weight, temperature, blood pressure (systolic and diastolic), heart rate, and respiration rate.

⁵ UPT must have minimum sensitivity of 25 mIU β -hCG/mL.

⁶ WOCBP include any female who has experienced menarche and who has not undergone successful surgical sterilization (hysterectomy, bilateral tubal ligation, or bilateral oophorectomy) or is not postmenopausal [defined as amenorrheal >12 consecutive months in women 50 years of age and older].

⁷ Treatment Area will be defined as a contiguous 25 cm² area on the face or scalp with at least four and no more than eight AKs.

⁸ Any "uncollected" test articles or subject diaries will be collected.

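### Does the mismatch between the sentence and the formula for Study Day in SAP section 6 put the per-protocol visit window in doubt?

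*SAP*

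**What the plan says.** SAP section 6 gives two anchors for one variable. The sentence reads "The study day is the day of study relative to the date of randomization (Baseline visit/Day 1", with the bracket closing there. The line below it reads "Study Day = follow-up visit date – first dose date + 1".

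The surrounding text bears on whether the two dates can differ:

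- The schedule (SAP section 5, and the same table in the protocol) labels Visit 1 as Day 1. It puts the "Treatment Period (at home") on Days 1–3, Visit 2 on Day 4 with no tolerance, and Visit 6 on Day 57 ± 2.
- Protocol 9.1 tells staff: "Instruct the subject to apply the test article once per day for three consecutive days at home". It does not say in terms that the first dose must fall on the date of Visit 1. Under the same section staff "Schedule Visit 2/Day 4 follow-up visit" before the subject leaves.
- Protocol 9.2 collects tubes and diary at Day 4. Its note allows that outstanding "test articles or subject diaries will be collected at Visit 3/Day 8".
- Protocol 17.3 admits to the PP population subjects who "completed the study within the designated visit window" of ±2 days and who "applied all three doses of the test article and no other evidence of material dosing noncompliance". It names no reference date for the window.

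Protocol 17.3.1 and SAP 8.6.1 make the PP population primary for equivalence. The text under SAP 8.2.3 (PP Population) and 8.3 (missing data) is not visible in the public copy. Nor are the subject instruction sheet and diary in the protocol appendices.

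**The concern.** A derived variable should have one definition. Here a subject who is randomised on one day and first doses on the next has two Study Days for every visit, and under the formula the Baseline visit becomes Day 0, against the sentence's own label of Day 1.

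A late start is possible. Dosing is at home, and protocol 9.1 advises against applying the gel straight after a shower or within two hours of bedtime, so an afternoon Visit 1 could lead to a next-day first dose. The visible dosing criterion for the PP population asks for three applications, not applications on particular calendar days.

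If the SAP's Study Day were the variable used to check the ±2-day window, then for late starters the choice of anchor would decide who enters the primary equivalence analysis.

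**Working it through.** **The plan's own figure.** Week 8 is 8 × 7 + 1 = Day 57, so the Visit 6 window is Days 55–59. Both definitions reproduce this when the first dose is taken on the day of Visit 1.

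**Effect of a lag.** Let L be the number of days from Visit 1 (randomisation) to first dose. Then

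day by formula = day by sentence − L,

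so the formula's window is Days 55 + L to 59 + L counted from Visit 1, and the two windows share max(0, 5 − L) days.

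| L | Formula window (days from Visit 1) | Days classified differently |
|---|---|---|
| 0 | 55–59 | none |
| 1 | 56–60 | 55, 60 |
| 2 | 57–61 | 55, 56, 60, 61 |
| 3 | 58–62 | 55, 56, 57, 60, 61, 62 |

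**Share of late starters affected.** The documents give no distribution of visit dates, so two are assumed: uniform over Days 55–59, and normal about Day 57 rounded to whole days.

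- L = 1: uniform, 1/5 = 20%. Normal with SD 1 day, 6.1% (Day 55) + 0.6% (Day 60) = 6.7%. SD 1.5 gives 14.9% and SD 2 gives 18.7%.
- L = 2: 30.9% (SD 1) to 40% (uniform, 2/5).

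**Subjects affected.** The protocol synopsis gives 480 subjects at 1:1:1, so 480/3 = 160 per arm, a ceiling for the PP population. The late-start rate is not in the documents; assume 2–10%, that is 3.2 to 16 subjects per arm.

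- All one day late: 3.2 × 0.067 = 0.2 to 16 × 0.20 = 3.2 per arm.
- All two days late: 3.2 × 0.309 = 1.0 to 16 × 0.40 = 6.4 per arm. This is less credible: the third dose would fall on Day 5, after the Day 4 visit at which tubes are collected.

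**Power.** Exact power for the planned 90% Wald interval with continuity correction, 50% clearance in both active arms (protocol 17.1) and a margin of 0.20 is 0.935 at 160 per arm, 0.937 at 158 and 0.921 at 157. The pattern is saw-toothed, as expected for a discrete outcome, and the loss is negligible.

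**Confidence limit.** The interval is d ± {1.645 × √[p₁(1−p₁)/n₁ + p₂(1−p₂)/n₂] + ½(1/n₁ + 1/n₂)}.

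- 80/160 v 80/160: 0 − (0.0920 + 0.0063) = −0.098.
- Three responders lost from Test only, 77/157 v 80/160: −0.0096 − (0.0924 + 0.0063) = −0.108.
- Three responders lost from Test and three non-responders from Reference, 77/157 v 80/157: −0.0191 − (0.0928 + 0.0064) = −0.118.

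Even these contrived losses move the limit by 1 to 2 percentage points. The second pattern needs reclassification to pick opposite outcomes in two blinded active arms, and nothing in the design suggests that it would.

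**Where Study Day is used.** In the visible text it appears only in SAP section 6.

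- Efficacy is defined by visit (SAP sections 3, 7.1.1 and 8.6.1).
- Local skin reactions are tabulated by visit (SAP 8.8.2).
- Treatment-emergent events are defined directly from the first dose date (SAP 7.2.1).
- The PP rule in protocol 17.3 refers to the designated window. The only windows designated are those in the schedule and protocol section 9, which start from Visit 1 = Day 1.

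**The case for a change.** The strongest case for a change is that the contradiction is certain and costs one line to remove. It could bear on the primary population, and a definition has to cover deviations as well as the planned case. An on-schedule Day 57 visit by a subject who started three days late would be Day 54 under the formula, and so outside the window. Even if the unseen SAP 8.2.3 fixes the PP reference date, section 6 still disagrees with itself.

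The disagreement stands, and whoever next edits the SAP should tidy it. The consequence does not stand as shown:

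- It requires Study Day to drive the window, and no visible text says so.
- It requires late starters to remain in the PP population. A third dose on or after the Day 4 collection visit departs from the schedule, and protocol 17.3 also excludes violations that bear on the treatment assessment. The Visit 3 note deals with items not yet handed in; it does not provide for later dosing.
- The instruction sheet and diary, which may say when to take the first dose, cannot be read here.
- Treatment codes stay blinded until the final database is locked (protocol section 7). Nothing visible suggests that the anchor would be chosen with knowledge of treatment.

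**Conclusion.** This is a clerical slip with no demonstrated effect on any planned analysis, so no change to the plan is called for. The sentence, the schedule and the booking of Visit 2 at Visit 1 all favour counting visits from Visit 1, and an analyst deriving visit windows would do that. First dose date keeps its own stated role for treatment-emergent events. Either anchor, applied consistently, gives a sound analysis.

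If Study Day did drive the PP window, about 0.2 to 3.2 subjects per arm would change status under the assumed 2–10% of one-day-late starts, or 1.0 to 6.4 if all of those were two days late. Power at 157 to 160 per arm stays between 0.921 and 0.937. No direction of bias is apparent, and an equivalence conclusion would be exposed only if the limit already lay very close to ±0.20.

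These sizes rest on assumed late-start rates and visit-date distributions that the documents do not supply. The conclusion also allows for the possibility that the unseen PP text already names the reference date.

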7 CLINICAL EVALUATIONS

7.1 Efficacy Measurements

7.1.1 AK Lesion Evaluation and Counting

AK lesion counts will be performed at Visit 1/Baseline, Visit 5/Day 29, and Visit 6/Day 57. At the Baseline Visit (Visit 1) all AK lesions in the selected contiguous 25 cm² Treatment Area, independent of size, will be identified, counted, recorded on the transparency, and measured for size (i.e., diameter). At Visits 5 and 6, the number of total AK lesions, independent of size, in the selected Treatment Area will be counted including Baseline AKs and new AKs; a new AK is defined as a lesion that was not present at Visit 1/Baseline.

The AK clearance rate within treatment area for a subject at post-baseline follow-up visits will be calculated as follows:

$$\left\{ 1 - \left[\frac{\#AKs \text{ at follow-up}}{\#AKs \text{ at Baseline}} \right] \right\} * 100.$$

Therefore, if the AK count at follow-up visits is 0, the clearance rate will be 100%, i.e., complete clearance of AK lesions.

7.2 Safety and Baseline Measurements

7.2.1 Adverse Events

An AE is defined as any untoward medical occurrence associated with the use of a drug in humans, whether or not considered drug related. A treatment emergent AE (TEAE) is defined as an AE that started on or after the first dose date.

Serious adverse events (SAE) are defined as any untoward medical occurrence that at any dose in the view of either the Investigator or Sponsor results in death, is life-threatening, requires inpatient hospitalization or prolongation of existing hospitalization, results in persistent or significant incapacity or substantial disruption of the ability to conduct normal life functions, or is a congenital anomaly/birth defect.

The severity of an AE will be recorded as mild, moderate or severe. The relationship between an AE and the test article will be classified as related, possibly related or not

related. The AE outcome will be specified as not recovered/resolved, recovered/resolved, recovered/resolved with sequelae, recovering/resolving, fatal, or unknown.

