14. ADVERSE EVENT REPORTING

14.1 Definitions

The following definitions will be utilized:

Adverse Event (AE) - Any untoward medical occurrence associated with the use of a drug in humans, whether or not considered drug related. AEs include any unintended sign, symptom, or disease that appears to worsen after the subject signs the informed consent for a clinical study. AEs may also include any changes in physical examination or laboratory parameters that are, in the investigator's opinion, clinically significant changes.

No causal relationship with the study drug is implied by the use of the term "adverse event". An exacerbation of a pre-existing condition/illness is defined as a more frequent occurrence or as an increase in the severity of the pre-existing condition/illness during the study. Planned or elective surgical procedures for pre-existing conditions that have not worsened are not AEs. However, any complication that occurs during a planned or elective surgery is an AE. Conditions leading to unplanned surgical procedures may also be AEs. If the event meets the criteria for a serious AE, such as an extended hospitalization, it will be considered a serious AE.

Serious Adverse Event (SAE) - Any AE that, in the view of either the investigator or the Sponsor, results in any of the following outcomes:

- Death
- Is life-threatening (Note: the term life-threatening refers to any AE that places the subject, in the view of either the investigator or Sponsor, at immediate risk of death. It does not include an AE that, had it occurred in a more severe form, might have caused death.)
- Inpatient hospitalization or prolongation of existing hospitalization

- A persistent or significant incapacity or substantial disruption of the ability to conduct normal life functions
- A congenital anomaly/birth defect
- Important medical events (Note: Important medical events refer to AEs that may not result in death, be life-threatening, or require hospitalization, may be considered a SAE when, based upon appropriate medical judgment, they may jeopardize the subject and may require medical or surgical intervention to prevent one of the outcomes listed in this definition.)

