14.3 Reporting of Adverse Events

AEs that occur from the time of informed consent through completion of the last study visit should be reported. Any SAE that the Investigator becomes aware of that occurs within 30 days of study completion or withdrawal should also be reported.

The investigator is responsible for reporting SAEs and AEs of special interest to the Institutional Review Board (IRB) according to agreements and instructions from that board or committee that oversees this research, as well as according to applicable regulations.

Any SAEs, AE of special interest, or pregnancy occurring in a subject receiving study drug must be reported to [REDACTED] within 24 hours of the site being informed of the event, even if the event does not appear to be drug-related. The report must be done by faxing or emailing the appropriate completed form (SAE Form or pregnancy reporting form) to [REDACTED]. Any pertinent follow-up information should be provided in a similar manner. [REDACTED] must then report the SAE to the Sponsor within 24 hours using the contact information below. The Sponsor will generate the MedWatch form and communicate it back to [REDACTED].

Actavis Inc.
Pharmacovigilance

[REDACTED]

The most common AEs reported with the use of ingenol mebutate gel include LSRs, application site pain, application site pruritus, application site irritation, application site infection, periorbital edema, nasopharyngitis, and headache. Less common AEs include eyelid edema, eye pain, and conjunctivitis. LSRs occurring within the Treatment Area will be assessed at each visit and documented as detailed in Section 10.2. Any LSR that requires medical intervention (prescription medication) or extends beyond the 2 cm surrounding skin should be documented as an AE.

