8.8 Safety Analyses

8.8.1 Adverse Events

AE terms will be coded into SOC and PT using MedDRA Coding Dictionary version 19.0. Tabulations of the number and percent of unique subjects reporting each TEAE will be presented by SOC, PT, and treatment group for (a) AEs, (b) serious AEs, (c) AEs by maximum severity, (d) AEs by closest relationship to study drug and (e) AEs within treatment area. AEs will be counted only once for a subject within each PT and SOC. If a subject reports a PT multiple times with differing severities/relationships to study medication, the subject is counted once for the PT with the maximum severity and the closest relationship, respectively.

All adverse events will be listed.

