8.12 Subgroup Analyses

No subgroup analyses are planned.

List of Tables:

Demographic and Baseline Characteristics

- 14.1.1 *Subject Disposition*
- 14.1.2 *Number of Subjects by Visit*
- 14.1.3.1 *Demographics (Safety Population)*
- 14.1.3.2 *Demographics (mITT Population)*
- 14.1.3.3 *Demographics (PP Population)*
- 14.1.4 *Baseline Vital Signs, Height, and Weight (mITT Population)*
- 14.1.5.1 *Baseline AK Count and Treatment Area (mITT Population)*
- 14.1.5.2 *Baseline AK Count and Treatment Area (PP Population)*
- 14.1.6 *Baseline Local Skin Reactions (Safety Population)*
- 14.1.7 *Medical History (mITT Population)*

Dosing Compliance and Exposure

- 14.2.1.1 *Dosing Compliance and Test Article Exposure (Safety Population)*
- 14.2.1.2 *Dosing Compliance and Test Article Exposure (mITT Population)*
- 14.2.2.3 *Dosing Compliance and Test Article Exposure (PP Population)*

Efficacy Data

- 14.3.1 *Complete Clearance Rates (PP and mITT Population)*
- 14.3.2.1 *AK Counts and Clearance Rates (mITT Population)*
- 14.3.2.2 *AK Counts and Clearance Rates (PP Population)*

Safety Data

- 14.4.1.1 *Local Skin Reaction – Erythema (Safety Population)*
- 14.4.1.2 *Local Skin Reaction – Flaking/Scaling (Safety Population)*
- 14.4.1.3 *Local Skin Reaction – Crusting (Safety Population)*
- 14.4.1.4 *Local Skin Reaction – Swelling/Edema (Safety Population)*
- 14.4.1.5 *Local Skin Reaction – Vesiculation/Pustulation (Safety Population)*
- 14.4.1.6 *Local Skin Reaction – Erosion/Ulceration (Safety Population)*
- 14.4.1.7 *Local Skin Reaction – Hyperpigmentation (Safety Population)*
- 14.4.1.8 *Local Skin Reaction – Hypopigmentation (Safety Population)*
- 14.4.1.9 *Local Skin Reaction – Scarring (Safety Population)*
- 14.4.2 *Summary of Adverse Events (Safety Population)*
- 14.4.3 *Treatment Emergent Adverse Events (Safety Population)*
- 14.4.4 *Treatment Emergent Adverse Events by Severity (Safety Population)*
- 14.4.5 *Treatment Emergent Adverse Events by Relationship to Test Article (Safety Population)*
- 14.4.6 *Treatment Emergent Adverse Events Occurring within the Treatment Area (Safety Population)*
- 14.4.7 *Concomitant Medications (Safety Population)*

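### The SAP's TEAE definition has no worsening clause, so an AE that starts before dosing and worsens afterwards may be missing from the TEAE tables

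*SAP*

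**What the plan says.** The only definition of a TEAE in the two documents is in SAP 7.2.1, where it is "defined as an AE that started on or after the first dose date". The protocol synopsis makes the incidence of TEAEs, with severity and causality, a safety endpoint but does not define the term.

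SAP 8.8.1 builds its summaries on that definition: "Tabulations of the number and percent of unique subjects reporting each TEAE will be presented by SOC, PT, and treatment group". It then names five sets: AEs, serious AEs, AEs by maximum severity, AEs by closest relationship, and AEs within the treatment area. It adds that "All adverse events will be listed". In the SAP's List of Tables, 14.4.3 to 14.4.6 carry treatment-emergent titles. Table 14.4.2 does not; its title begins "Summary of Adverse Events (Safety Population", and neither document describes its content.

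Collection starts before dosing. Protocol 14.3 states that "AEs that occur from the time of informed consent through completion of the last study visit should be reported". The Schedule of Events in both documents allows screening up to 30 days ahead of Baseline for subjects who need washout. The others may have both done at one visit.

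On worsening, Protocol 14.1 says that "AEs include any unintended sign, symptom, or disease that appears to worsen after the subject signs the informed consent for a clinical study". It also describes an exacerbation of a pre-existing condition, "defined as a more frequent occurrence or as an increase in the severity of the pre-existing condition/illness during the study". SAP 7.2.1 restates the AE definition without the sentence on worsening.

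**The concern.** A treatment-emergent table should show what appeared or got worse once treatment began. A rule based only on start date captures the first kind of event and not the second. An AE that starts mild during washout and becomes severe or serious after the first application could keep its pre-dose start date and so fail the definition.

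The study objective includes safety, and the TEAE tables are where Test, Reference and Vehicle are set side by side. A missing worsening would understate post-dose events there. Because serious AEs are usually few, a single one could be a visible share of its table.

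The SAP is also narrower here than the protocol. Protocol 17.3.2 plans to summarize all reported AEs by class, term, severity and relationship, whereas SAP 8.8.1 frames those tabulations as TEAE tabulations.

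**Working it through.** The documents state no figure on this point, so there is none to reproduce. The check is to apply the SAP rule (TEAE if the start date is on or after the first dose date) to each way an event could be recorded, and to follow it to the planned output.

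1. **AE starts between consent and first dose, worsens or becomes serious after dosing, and is kept as one record.** The start date precedes first dose, so it is not a TEAE. It is absent from the SAP 8.8.1 tabulations and from Tables 14.4.3 to 14.4.6. It is present in the listing of all AEs. Table 14.4.2 cannot be determined.
2. **Same event, with the worsening entered as a separate AE.** The new record starts after first dose, so it is a TEAE and is tabulated.
3. **Medical-history condition that worsens after dosing and is recorded as an AE.** The AE starts after first dose, so it is a TEAE.
4. **One of the nine listed LSRs worsens from Baseline.** It appears by visit and severity in Tables 14.4.1.1 to 14.4.1.9, whatever its TEAE status.
5. **AE starts on the first dose date but before the application.** It counts as a TEAE, because the rule compares dates only.

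Only the first case loses information, and the documents do not say whether the first or the second applies. Cases 4 and 5, together with the option of a combined Screening and Baseline visit, confine the exposure mainly to subjects with a washout interval.

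**Size.** Nothing in the documents gives a rate, so every rate below is an assumption. Let w be the fraction of subjects with a washout interval, a the fraction of those with an AE between consent and first dose, and b the fraction of those AEs that worsen or become serious after dosing. With N = 480 (planned enrollment, protocol synopsis), the expected number affected is N × w × a × b, if every such worsening is kept as one record.

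- a = 5%, b = 10%, w = 100%: 480 × 1 × 0.05 × 0.10 = 2.4. At the 1:1:1 allocation in the synopsis this is 2.4 / 3 = 0.8 per arm.
- a = 5%, b = 10%, w = 25%: 480 × 0.25 × 0.05 × 0.10 = 0.6.
- Low end, a = 1%, b = 5%, w = 25%: 480 × 0.25 × 0.01 × 0.05 = 0.06.
- High end, a = 10%, b = 20%, w = 25%: 480 × 0.25 × 0.10 × 0.20 = 2.4.

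The high rates with w = 100% would give 480 × 0.10 × 0.20 = 9.6, but that treats every subject as having a washout interval. A fair summary is roughly 0 to 3 of 480.

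**The case against.** The strongest reply is that the protocol already handles this. The sentence on worsening in Protocol 14.1 is not limited to pre-existing conditions, so a post-dose worsening can be read as an AE in its own right. Recorded that way, it has a post-dose start and meets the SAP definition. Recording practice may also be settled in the eCRF or its completion guidance; the eCRF is cited in SAP section 1 but is not among the documents reviewed. The expected skin reactions have their own tables, and an event that becomes serious goes to safety review within 24 hours under Protocol 14.3.

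Much of this stands. The loss is conditional, and the reactions most expected from a topical gel are largely protected. But the protocol permits a separate record without requiring one. Its sentence on exacerbation concerns conditions that pre-date the study and does not tell a site what to do when an AE already recorded in the study gets worse. Protocol 14.3.4.1 sends new information on an ongoing SAE as a follow-up report, which leans toward a single record. Expedited reporting does not place an event in a table.

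A reader might infer something stronger: that such events are left out of all the AE tables. The documents do not support that. Table 14.4.2 is not titled as a TEAE table, and Protocol 17.3.2 promises a summary of all reported AEs. No listed table is titled for serious AEs, so 14.4.2 may be where they are meant to go, although that is an inference and SAP 8.8.1 frames its serious-AE tabulation as TEAE-based.

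**Conclusion.** The gap is real but small. The definition lacks a worsening clause and the recording rule is unstated. Whether a post-dose worsening of a pre-dose AE reaches the TEAE tables therefore depends on how each site enters it. If it is kept as one record, it is missing from the SAP 8.8.1 tabulations and is certain to appear only in the listing.

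The estimate of roughly 0 to 3 subjects rests entirely on assumed rates for washout, pre-dose AEs and later worsening; the documents supply none of them. The equivalence and superiority analyses are not touched. This is an improvement worth making, not a flaw that threatens the trial's conclusions.

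**What to change.** In SAP 7.2.1, define a TEAE as an AE that started, or that increased in severity or became serious, on or after the first application.

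To make this programmable, instruct sites that when an AE recorded before dosing worsens or becomes serious afterwards, the change is entered as a new AE record with its own start date. A single record with one start date would not show when the change happened, so the clause alone is not enough; a new record avoids adding a date-of-change field to the existing eCRF. The SAP 8.8.1 rule of counting a subject once per preferred term already prevents double counting.

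Add one line stating whether Table 14.4.2 covers all AEs or only TEAEs.

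The cost is a site data-entry instruction, a short SAP edit and minor programming. The edit should be made before unblinding, so that it is not a post-hoc redefinition.
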